11.3.2 Shifts Between Normal and Abnormal for Laboratory Tests

Laboratory observations will be categorized as normal, low, or high relative to the reference (normal) range associated with the laboratory that performed the assay. For each hematology, chemistry and urinalysis variable with a reference range, shift tables will be prepared for shifts from baseline to lowest, highest and final value during the entire study for each treatment group and ABBV-8E12 Overall. No comparisons of treatment groups will be performed. Shift tables will also be prepared by geographical region. The tables will present:

- The numbers and percentages of subjects with low or normal observations at baseline who have a high observation at any post-baseline visit
- The numbers and percentages of subjects with normal or high observations at baseline who have a low observations at any post-baseline visit
- The numbers and percentages of subjects with low or normal observations at baseline who have a high observation at the final visit
- The numbers and percentages of subjects with normal or high observations at baseline who have a low observations at the final visit

11.3.3 Potentially Clinically Significant Laboratory Values

Criteria for potentially clinically significant (PCS) values have been predefined for selected laboratory variables as outlined in [Appendix A](#). For each variable, a summary of

the number and percentage of subjects in each treatment group who have at least one double-blind observation that meets the PCS criteria and is more extreme than their baseline value will be provided. A listing will also be prepared that will include, for each variable, all observations for each subject that met the PCS criteria for that variable at any time during the study. PCS analysis for laboratory values will also be prepared by geographical region. No comparisons of treatment groups will be performed.

11.4 Analysis of Vital Signs and Weight

Vital sign variables include: diastolic blood pressure (DBP), systolic blood pressure (SBP) and pulse rate at supine and standing positions, orthostatic diastolic blood pressure, orthostatic systolic blood pressure, orthostatic pulse rate, and body temperature. The calculations of orthostatic vital sign values are:

- Orthostatic SBP (mmHg) = Standing SBP – Supine SBP
- Orthostatic DBP (mmHg) = Standing DBP – Supine DBP
- Orthostatic Pulse Rate (bpm) = Standing Pulse Rate – Supine Pulse Rate.

Weight variables include weight and BMI.

11.4.1 Vital Sign and Weight Mean Changes

Diastolic blood pressure, systolic blood pressure and pulse will be analyzed separately for each position of measurement. Analyses of mean change from baseline to each double-blind visit value and to the minimum, maximum and final double-blind value will be presented for each vital sign and weight variable. Analyses of mean change from final double-blind value to each post-treatment visit will also be presented for vital sign variable.

For each mean change analysis, the mean and median change will be presented for each treatment group. The mean change for each ABBV-8E12 dose group will also be compared to the mean change for the placebo group using an ANOVA with treatment as

the factor. *P* values and 95% confidence intervals will be calculated based on pairwise contrasts within the ANOVA.

11.4.2 Potentially Clinically Significant Vital Sign and Weight Values

Criteria for potentially clinically significant values have been predefined for selected vital sign and weight variables as outlined in [Appendix B](#). For each variable, a summary of the number and percentage of subjects in each treatment group who have at least one double blind observation that meets the PCS criteria and is more extreme than their baseline value will be provided. A listing will also be prepared that will include, for each variable, all observations for each subject that met the PCS criteria for that variable at any time during the study. PCS analysis for vital sign and weight will also be conducted by geographical region. No comparisons of treatment groups will be performed.

11.5 Analysis of Electrocardiogram (ECG) Variables

Electrocardiogram (ECG) variables include: heart rate (HR), PR interval, QRS interval, uncorrected QT interval, and QT interval corrected for heart rate using Fridericia's formula (QTcF).

11.5.1 ECG Mean Changes

Analyses of mean change from baseline to each double-blind visit value and to the minimum, maximum and final double-blind value will be presented for each ECG variable. Analyses of mean change from final double-blind value to final post-treatment value will also be presented for each ECG variable.

For each mean change analysis, the mean and median change will be presented for each treatment group. The mean change for each ABBV-8E12 dose group will also be compared to the mean change for the placebo group using an ANOVA with treatment as the factor. *P* values and 95% confidence intervals will be calculated based on pairwise contrasts within the ANOVA.

11.5.2 Potentially Clinically Significant ECG Values

Criteria for potentially clinically significant values have been predefined for selected ECG variables as outlined in [Appendix C](#). For each variable, a summary of the number and percentage of subjects in each treatment group who have at least one double-blind observation that meets the PCS criteria and is more extreme than their baseline value will be provided. Listings will also be prepared to include all observations for each variable for each subject that met the PCS criteria for that variable at any time during the study. PCS analysis for ECG values will also be conducted by geographical region. No comparisons of treatment groups will be performed.

11.6 Analysis for Other Safety Variables

11.6.1 Columbia-Suicide Severity Rating Scale (C-SSRS)

Number and percentage of subjects in the following categories will be summarized for each treatment group and ABBV-8E12 Overall by visit and for the entire study:

- Answered 'Yes' to each C-SSRS item
- Had suicidal ideation (defined as answering 'Yes' to one or more suicidal ideation items)
- Had suicidal ideation only (defined as answering 'Yes' to one or more suicidal ideation items and answering 'No' to all suicidal behavior items)
- Had suicidal behavior (defined as answering 'Yes' to one or more suicidal behavior items)
- Had suicidal ideation or behavior (defined as answering 'Yes' to one or more suicidal ideation or behavior items)

11.6.2 Analysis of CSF Safety Parameters

CSF safety variables include RBC and WBC with differential, total protein, albumin, glucose and IgG. Analyses of mean change from baseline to Week 14 (Cohort 1 subjects only) and mean change from baseline to final double-blind value will be presented for each CSF safety variable.

For each mean change analysis, the mean and median change will be presented for each treatment group. The mean change for each ABBV-8E12 dose group will also be compared to the mean change for the placebo group using an ANOVA with treatment as the factor. *P* values and 95% confidence intervals will be calculated based on pairwise contrasts within the ANOVA.

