Region	Cohort 1*	Cohort J1**	Cohort 2***
Global (not including Japan)	First 30 subjects enrolled [#]	NA	n = ~276
Japan	NA	First 9 subjects enrolled [#]	n = ~15

* Cohort 1: Augmented safety and PK assessments in the first 30 subjects enrolled into the global study from countries other than Japan.

** Cohort J1: Augmented safety and PK assessments in the first 9 subjects enrolled into the study from Japan.

*** Cohort 2: All other subjects enrolled in the global study not participating in Cohort 1 or Cohort J1.

Augmented safety and pharmacokinetic assessments including additional study visits, more frequent neurological exams, vital signs, blood collections for safety labs, an additional lumbar puncture and MRI, and additional monitoring by the Data Monitoring Committee (DMC) will be performed in Cohort 1 and Cohort J1.

Eligible subjects will be enrolled into the Treatment Period of the study on Day 1 and receive their first infusion of study drug. During the first 4 weeks, subjects will have 3 study drug infusions; the first on Day 1, the second on Day 15, and the third on Day 29; thereafter, subjects will return to the study site every 28 Days for their study drug infusion, blood collection, study procedures and assessments as outlined in the Study Activities Table (Appendix C). This dosing schedule (with one additional dose delivered at Day 15) will enable rapid attainment of steady-state drug levels in plasma to maximize the likelihood of demonstrating a treatment effect. Subjects will be observed on-site for at least 2 hours following each of the first 4 infusions of study drug and for at least 30 minutes after the end of infusion of all doses thereafter. Subjects randomized in Cohort 1 and Cohort J1 will return to the study site on Day 5, Day 15, Day 89, Day 99, and Day 113 for collection of additional safety assessments and PK samples listed in Table 4 (Safety and PK Procedures for Cohort 1 and Cohort J1).

Subjects in Cohort J1 will be confined for a minimum of 24 hours following their first infusion. For subjects expecting to be discharged on the second day (Day 2), the Investigator will assess safety to determine discharge. Subjects will have another study visit 2 days after the first infusion (Day 3), either while in the hospital or as an outpatient to assess safety. From their second to fourth infusion, Cohort J1 subjects will be observed on-site for at least 2 hours following each infusion of study drug.

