5.2.2 Exclusion Criteria

A subject will not be eligible for study participation if he/she meets any of the following criteria:

1. Male or female subject weighing less than 44 kg (97 lbs.) at screening will be excluded.
2. Mini-Mental State Examination (MMSE) score less than 15 at screening, or cognitive impairment that in the Investigator's opinion would preclude collection of outcome measures. In Germany, for all subjects with an MMSE score of 24 or less

at the time of study entry, an evaluation by an independent psychiatrist will also be requested. If, in the opinion of the independent psychiatrist, subject is unable to provide consent independently, the subject will not be enrolled in the study.

3. Any contraindication or inability to tolerate brain MRIs (e.g., a pacemaker or any other implanted device or condition that would preclude proximity to a strong magnetic field).
4. During enrollment of Cohort 1 and Cohort J1, any contraindication or inability to tolerate lumbar punctures (LP) (e.g., use of anticoagulant medications such as warfarin) are exclusionary. During enrollment of Cohort 2, subjects who are not able to undergo LP may be admitted with permission of the AbbVie Medical Director, and these subjects will not be required to undergo LP during the study.
5. Subject resides at a skilled nursing or dementia care facility, or admission to such a facility is planned during the study period.
6. Evidence of any neurological disorder that could explain signs of PSP, including:
 - a. Signs of idiopathic Parkinson's disease (e.g., severe asymmetric parkinsonian signs, clinically significant tremor at rest, or prominent and sustained response to levodopa therapy)
 - b. Signs of multiple system atrophy (MSA) (e.g., prominent early cerebellar limb ataxia or unexplained symptomatic autonomic dysfunction)
 - c. Signs of Lewy body disease (e.g., hallucinations or delusions unrelated to dopaminergic therapy or other illness)
 - d. Probable Alzheimer's disease according to National Institute of Neurological and Communicative Disorders and Stroke and the Alzheimer's Disease and Related Disorders Association (NINCDS-ADRDA) criteria
 - e. History of repeated strokes with stepwise progression of parkinsonian features
 - f. History of major stroke
 - g. History of severe or repeated head injury
 - h. History of encephalitis

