The above listed imaging sequences may be adapted, sequences may be dropped or additional imaging sequences may be included based on feasibility. The duration of each imaging session is not expected to exceed 60 minutes. Details of the MRI procedures will be described in the MRI Procedures Manual provided by the Sponsor. The 3D T1 weighted sequences will also be acquired for volumetric analysis that will enable a quantitative assessment of whole brain volume and regional brain volume.

Scans at all protocol-required time points, including at screening, that are of poor quality (e.g., due to subject motion during the scan, inadequate coverage of the brain, improper positioning of the head, use of incorrect scan or geometry parameters or noisy image) as determined by the MRI technologist at the imaging center or reviewing radiologist or

Sponsor will be repeated at the earliest possible time but within 15 days of the protocol-required time point to obtain a scan of good quality.

On-treatment MRIs will be performed at the time points indicated in the Study Activities Table ([Appendix C](#)). The time window for the MRI procedure at each protocol-required time point is ± 7 days.

Sedation is not recommended but is allowed. Subjects who might need sedation should discuss this with the principal investigator prior to the imaging procedure. If sedation is required it should occur after all scales and cognitive testing have been performed or, if this is not possible, at least 48 hours before the testing.

The MRI technician is responsible for performing brain MRI scans at all protocol-required time points.

Lumbar Puncture (LP)

For all subjects, LPs to collect cerebrospinal fluid (CSF) will be performed at time points indicated in the Study Activities Table ([Appendix C](#)).

Subjects in Cohort 1 and Cohort J1 will undergo a LP at the following time points:

- Screening – To be done after all other entry criteria have been satisfied.
- Day 99
- Premature Discontinuation or Week 52 (Completion Visit/Premature Discontinuation) – if at least 3 months after the previous LP.

Subjects in Cohort 2 will undergo a LP at the following time points.

- Screening – To be done after all other entry criteria have been satisfied.
- Premature Discontinuation or Week 52 (Completion/Premature Discontinuation Visit) – if at least 3 months after the previous LP.

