A sample of CSF will be collected according to the Collection and Processing of CSF Samples manual provided to the study site by the Sponsor. If sampling is not successful or is standard of care for the institution, other methods including CT/fluoro guided or ultrasound guided lumbar puncture can be used at the discretion of the local clinical site staff. CSF clinical labs will be analyzed locally at the applicable clinical site after each lumbar puncture/CSF collection. These measures include cell counts (red blood cell [RBC] and white blood cell [WBC] with differential), total protein, albumin, and glucose (Refer to [Table 6](#) for Clinical Laboratory Tests). If the local laboratory is unable to perform some of the CSF measurements, samples may be sent to the Central Laboratory for analyses of Total Protein, Albumin, and Glucose only. Other CSF measurements (e.g., ABBV-8E12 concentration, tau and other exploratory biomarkers) will be analyzed by the applicable designated laboratory or at AbbVie.

Cohort 2 subjects who are not able to undergo a LP may be enrolled with permission of the AbbVie Medical Director without the requirement of a LP during the study.

Headaches may occur following withdrawal of CSF. Subjects may be treated with the following: IV hydration, IV caffeine administration, bed-rest and analgesics.

Uncommonly a blood patch (injection of some of the subject's blood to patch the CSF leak) may be needed. Potential but rare risks of lumbar puncture include infection, damage to nerves in the back, and bleeding into the CSF space. The risk of these is much less than 1%.¹¹ Institutional policy and investigator discretion should be followed to provide the appropriate post-lumbar puncture observation period, and to provide information to the patient on possible side effects and limitations on strenuous physical activity and driving.

Diagnostic Tools and Rating Scales

Prior to the start of the study, designated raters will be certified in the use of all scales used in this study. The objective of this certification/training is to establish uniformity across sites in the administration, interpretation and scoring of these rating instruments. Raters who cannot participate in pre-study certification/training or raters who become

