The first 30 subjects enrolled into the study in countries not including Japan will be represented as Cohort 1 in this protocol while the first 9 Japanese subjects enrolled into the study will compose Cohort J1. Subjects enrolled subsequent to Cohort 1 and Cohort J1 will be represented as Cohort 2. Augmented safety and pharmacokinetic monitoring including additional study visits, more frequent neurological exams, vital signs, blood collections for safety labs, an additional lumbar puncture and MRI, and additional monitoring by the DMC will be performed in Cohorts 1 and J1.

A schematic of the study design is shown below in [Figure 1](#).

Figure 1. Study Schematic

[figure not shown]

Table 1. Safety and PK Procedures for Cohort 1 and Cohort J1

	Screening		Cohort 1 and Cohort J1, Doses 1 – 5										
	Visit 1	Visit 2	Dose 1			Dose 2	Dose 3	Dose 4	Dose 5			Dose 6	
Weeks of Study Drug Exposure	N/A	N/A	0	0	0	0	2	4	8	12	13	14	16
	Days –56 to –8	Days –56 to –8	Day 1	Day 2 ^{h,k}	Day 3 ^j	Day 5	Day 15	Day 29	Day 57	Day 85	Day 89	Day 99	Day 113
Physical Exam ^a	X		X	X	X								
Neurological Exam	X		X	X	X	X	X	X	X	X		X	
Orthostatic Vital Signs	X	X	X	X	X	X ^c	X ^b	X ^d	X ^d	X ^b	X	X	X
12-Lead ECG	X		X ^b				X ^b	X ^d	X ^d	X ^b			
Clinical Laboratory Tests	X		X				X ^j	X	X	X			
MRI	X						X ^e			X		X ^f	
Lumbar Puncture/ CSF Sample Collection	X												
PK Sample Collection			X ^g			X	X ^g	X	X	X ^g	X	X	X
ADA Sample Collection			X ^h				X ^h	X ^h	X ^h	X ^h	X	X	X
C-SSRS	X	X	X			X	X	X	X	X	X	X	X
AE/ ConMed Review	X	X	X	X	X	X	X	X	X	X	X	X	X
24 hour confinement ^l			X										

- a. Additional symptom-driven physical exams can be performed as needed.
- b. Pre-dose and within 15 minutes after the end of the infusion and prior to the PK sample collection.
- c. Collection should be scheduled as close as possible to the corresponding time of the post infusion PK collection on Day.
- d. Pre-dose (just prior to the start of infusion).

Table 1. Safety and PK Procedures for Cohort 1 and Cohort J1 (Continued)

- e. For subjects in Cohort 1 and Cohort J1, an MRI will be performed within 2 weeks following the second dose and results must be available prior to the next scheduled dose.
- f. The lumbar puncture will be performed approximately 14 days after the fifth dose.

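### The Week 14 CSF safety analysis is limited to Cohort 1, although Cohort J1 has the same Day 99 lumbar puncture and CSF safety tests

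*SAP*

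**What the plan says.** SAP 11.6.2 (Analysis of CSF Safety Parameters) plans two comparisons for each CSF safety variable. One is "mean change from baseline to Week 14 (Cohort 1 subjects only"). The other is the change from baseline to the final double-blind value, with no cohort limit. Each dose is compared with placebo in an ANOVA with treatment as the only factor.

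SAP 4.2 defines the cohorts so that they do not overlap. Cohort 1 is made up of 30 subjects, all from outside Japan. For Japan, the SAP says that "the first 9 Japanese subjects enrolled into the study will compose Cohort J1".

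The sampling schedule treats the two cohorts alike:

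- Protocol 5.3.1.1, Lumbar Puncture: "Subjects in Cohort 1 and Cohort J1 will undergo a LP at the following time points". The list that follows is screening, Day 99, and Week 52 or premature discontinuation.
- SAP 4.2, Table 1, headed for both cohorts: "The lumbar puncture will be performed approximately 14 days after the fifth dose". SAP Table 2 also marks the Day 99 puncture for both.
- Protocol 5.3.1.1, on the safety tests: "CSF clinical labs will be analyzed locally at the applicable clinical site after each lumbar puncture/CSF collection".

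**The concern.** Cohort J1 subjects have an extra lumbar puncture at Week 14, and their CSF is tested for safety. The SAP's Week 14 analysis of those tests then leaves them out. The information comes from an invasive procedure, and the protocol justifies more frequent assessment in both early cohorts by the need to pick up safety signals promptly (Protocol 5.6.2).

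Day 99 is the only scheduled on-treatment puncture before Week 52 or discontinuation. The Week 14 comparison is therefore the SAP's one CSF safety summary at a fixed earlier visit. As written, it contains no Japanese subjects and is less precise than the collected data allow. SAP 14.0 says safety analyses by geographical region were added once Japan joined the study, so the omission also runs against the SAP's own direction.

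**Working it through.** **Inputs**

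- Cohort 1: 30 subjects, none from Japan (SAP 4.2).
- Cohort J1: 9 subjects. Protocol 5.1, Table 1 notes: "Augmented safety and PK assessments in the first 9 subjects enrolled into the study from Japan".
- Dose 5 on Day 85; extra puncture on Day 99 (SAP Tables 1 and 2).
- Randomisation 1:1:1 within Japan (SAP 5.2).

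**Plan's own figure.** Protocol 5.6.4 gives 39 subjects for the two initial cohorts together. 30 + 9 = 39, which agrees.

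**Is Day 99 the Week 14 visit?** 99 − 85 = 14 days after Dose 5, and (99 − 1)/7 = 14.0 weeks after Day 1. Yes.

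**Are all nine J1 subjects meant to have this puncture?** Yes. Protocol 5.2.2, criterion 4, reads "During enrollment of Cohort 1 and Cohort J1, any contraindication or inability to tolerate lumbar punctures (LP") and makes this exclusionary. Only Cohort 2 subjects can be admitted without the puncture.

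**How many are left out?** Planned with a Day 99 puncture: 39. Planned in the Week 14 CSF safety analysis: 30. Omitted: 9, and 9/39 = 23.1%. At 1:1:1 that is 9/3 = 3 per arm.

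**Effect on precision.** The documents give no SD for any CSF variable, so results are in SD units. Assume equal arms, complete data, a common variance and no difference between regions in mean change. The standard error of a dose-placebo difference is SD × √(2/n), with n per arm and 3n − 3 error degrees of freedom.

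| | Cohort 1 only | Cohorts 1 and J1 |
|---|---|---|
| Total planned | 30 | 39 |
| n per arm | 10 | 13 |
| Error df | 27 | 36 |
| SE (SD units) | √(2/10) = 0.447 | √(2/13) = 0.392 |
| 95% CI half-width (SD units) | 0.918 | 0.795 |

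Ratio of standard errors: √(10/13) = 0.877, a reduction of 12.3%.

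**How the SAP treats J1 elsewhere**

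- SAP 13.0 (biomarkers): the Week 14 row of the timing table covers Cohorts 1 and J1.
- SAP 12.2 (PK tabulations): the CSF concentration summary after the fifth dose names Cohort 1 only. Protocol 8.1.7.1 names both cohorts for the same summary.
- SAP 6.2 (vital sign and C-SSRS windows): the introductory text makes the first 30 randomised subjects Cohort 1 and everyone else Cohort 2, yet the windows listed below it include J1.
- SAP 14.0: records that Japan and the larger sample size came in with Amendment 3.

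This pattern suggests wording that was not updated when J1 was added, rather than a decision to exclude. The documents do not say which.

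**The case against.** The mismatch with the schedule is not in dispute. The case on the other side is that it matters very little.

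- **Surveillance does not depend on this table.** CSF tests are run locally after each puncture, and investigators follow up out-of-range laboratory values. The DMC reviews available unblinded safety data at about 80, 130, 180, 240 and 330 randomised subjects and every six months thereafter. None of this excludes J1. This stands: the omission affects a planned SAP summary, not real-time oversight.
- **The data are not lost altogether.** J1 subjects remain in the baseline-to-final analysis. A J1 Day 99 result can itself be the final value if no later puncture is done and it meets the 45-day rule in SAP 6.2. This also stands; the loss is at the Week 14 analysis.
- **Nine and 12% are upper figures.** Discontinuation or a missed puncture lowers the count. If a local laboratory cannot run the tests, only total protein, albumin and glucose go to the central laboratory, so cell counts may be missing. A regional difference in mean change would enter the residual error of the treatment-only ANOVA and reduce the gain. No power target or decision rule is attached to this comparison. All of this stands.
- **It is stale text, not an analysis choice.** That is probably how it arose. But a programmer following 11.6.2 would still exclude J1, and the reported Week 14 estimates would differ. The protocol's safety analysis section specifies no CSF mean-change analysis that would settle the population instead.

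**Conclusion.** The point holds. As written, SAP 11.6.2 drops all of Cohort J1 from the Week 14 CSF safety analysis without giving a reason. It conflicts with the sampling schedule in both documents and differs from the SAP's own handling of Week 14 in the biomarker section. The size is 9 of 39 planned subjects (23%). The standard error could be about 12% smaller with J1 included, given balanced arms, complete data, common variance and no regional difference. The consequence is minor and confined to one safety summary: no efficacy result, error rate or stopping rule depends on it. It is worth correcting because the data are already scheduled to be collected.

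**What to change.** In SAP 11.6.2, change the parenthesis to *Cohort 1 and Cohort J1 subjects only*, matching SAP 13.0. If leaving J1 out is intended, state the reason.

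Three related edits belong in the same revision:

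- Name Cohort J1 in SAP 12.2, in line with Protocol 8.1.7.1.
- Correct the sentence in SAP 6.2 that assigns everyone after the first 30 randomised to Cohort 2.
- State the Week 14 window for CSF safety tests. The clinical laboratory windows in SAP 6.2 are for Weeks 2, 4, 8, 12, 24, 48 and 52, and the Week 14 condition in SAP 13.0 is written for tau variables.

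The cost is a few words in the SAP. No visit, procedure, sample or protocol change is needed.
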